8.7.3 Analysis of Primary Endpoints for Phase 1/2/3a, Phase 3b and Phase 3c

8.7.3.1 Main Estimation of Primary Immunogenicity Endpoint for Phase 1/2/3a Substudy (Estimand 1)

The primary immunogenicity endpoint for Phase 1/2/3a and the primary immunogenicity noninferiority endpoint for Phase 3c-1 will be evaluated in the Phase 1/2/3a IAS and Phase 3c-1 IAS respectively.

- For Phase 1/2/3a it is defined as the proportion of participants in each study vaccine group that demonstrate seroconversion (defined as: 4-fold increase in titer from baseline) by surrogate virus NAb assay at Day 57. The lower bound of the 95% CI for SC¹⁵⁴ will be used for evaluation of ARCT-154- vs placebo-treated participants (Section 8.3.1).
- For Phase 3c it is defined as the geometric mean ratio (i.e., the ratio of geometric mean concentration for ARCT-154 / ChAdOx1 nCoV-1) by pseudovirus microneutralization test at Day 57.
- International units (i.e., the WHO/NIBSC international reference standard) will be used if available.

Seroconversion is defined as at least 4-fold increase of post-study intervention antibody titers from the baseline titer or from half of the LLOQ if undetectable at baseline. GMT ratio is defined as geometric mean of fold increase of post-study intervention titers over the baseline titers.

Geometric mean concentration (GMC) is the geometric mean of the antibody concentrations of all participants in each treatment arm; geometric mean ratio (GMR) is the ratio of geometric mean concentrations for the two study vaccines being compared, and geometric mean fold rise is the geometric mean of the proportional rise in GMC from baseline. These will be calculated as follows:

$$GMC = \ln^{-1}\left(\frac{\sum_{i=1}^n \ln X_i}{n}\right), \text{ where } X: \text{antibody titer}$$

$$GMR = \frac{GMC_{vaccine\ 1}}{GMC_{vaccine\ 2}}$$

$$GMFR = \ln^{-1}\left(\frac{\sum_{i=1}^n \ln \left(\frac{X_2}{X_1}\right)}{n}\right), \text{ where } X_2 \text{ is the antibody concentration at time point of evaluation and } X_1 \text{ is the antibody concentration at the reference time point (for example baseline)}$$

For SCR, chi-square or Fisher's exact test will be used to perform comparison of the two treatment arms. 95% CI of the SCR will also be presented. Pearson's Chi-square test will be used except for the case of small cell count (less than 5).

Definition and handling of intercurrent events is described in Section 8.3.1.

8.7.3.2 Main Estimation of Primary Safety Endpoint for Phase 1/2/3a, 3b, and 3c (Estimand 3 & 4)

Summaries of the number of participants (%) with solicited AEs, unsolicited AEs, MAAEs, SAEs, and AEs leading to discontinuation/withdrawal will be presented. Unsolicited events will be presented overall and with a focus on those related to vaccine administration. All summaries will be evaluated by study group.

As summarized in [Table 18](#), the Clopper-Pearson 95% CIs will be presented for the incidence rate of solicited AEs, unsolicited AEs, SAEs, MAAEs, and AEs leading to discontinuation/withdrawal, as well as those that are considered related (possibly, probably, or definitely) to study vaccine.

Solicited AEs will be analyzed in the RAS and unsolicited AEs, MAAEs, AE/SAEs will be summarized in the SAS relevant to the Phase of the study being evaluated ([Section 8.2](#)).

8.7.3.3 Supportive Analysis of Primary Safety Endpoints for Phase 1/2/3a, 3b, and 3c (Estimand 3 & 4)

Analysis of safety, as described [Section 8.7.3.2](#) and [Table 18](#) will be performed for a number of different time intervals. Evaluation may also be performed by the stratification factors described in [Section 8.6](#).

The number and percentage of participants with any solicited AEs (local injection site and systemic events) before and after each vaccination will be reported, including summaries by grade ([Appendix 4](#)). The number and percentage of participants with unsolicited AEs will be reported, including summaries by severity (mild/moderate/severe). The number and percentage of SAEs and MAAEs will be summarized by incidence. The incidence rate of these events will be presented with 2-sided 95% CIs using the Clopper-Pearson method.

Solicited AE will be analyzed in the RAS and unsolicited AEs, MAAEs, AEs leading to discontinuation/withdrawal, SAEs will be summarized in the SAS relevant to the Phase of the study being evaluated ([Section 8.2](#)).

Adverse events after to any non-study vaccination will be analyzed accordingly as a supportive analysis.

8.7.3.4 Main Estimation of Phase 3b Primary Efficacy Endpoint (Estimand 2)

This endpoint is the incidence rate of virologically confirmed COVID-19. The main analysis on this endpoint will be carried out in the Phase 3b mITT and the sensitivity analysis will be performed in the Phase 3b PP analysis set. Incidence rate in each arm will be displayed together with 95% CI.

The statistical hypothesis for this analysis is described in [Section 8.4.2](#).

Definition and handling of intercurrent events is described in [Section 8.3.1](#).

8.7.4 Analysis of Secondary Endpoints for Phase 1/2/3a, Phase 3b and Phase 3c

8.7.4.1 Main Estimation of Secondary Immunogenicity Endpoints for Phase 1/2/3a and Phase 3c Substudies

Secondary endpoints will be evaluated in participants in Phases 1, 2 and 3a (the Immunogenicity Subgroup) and Phase 3c-1 (the Immunogenicity Noninferiority Subgroup) who have no evidence of early infection (Section 8.3.1) and have received two doses of study vaccine (ARCT-154 or placebo for Phase 1/2/3a; ARCT-154 or ChAdOx1 for Phase 3c) in the initial vaccination series. International units (i.e., the WHO/NIBSC international reference standard) will be used if available, and comparisons will be based on lower bound of the 95% CI.

Definition and handling of intercurrent events is described in Section 8.3.1.

8.7.4.2 Main Estimation of Secondary Efficacy Endpoints for Phase 3b

These will be evaluated in the Phase 3b mITT using the same testing methods as for the Phase 3b primary efficacy endpoint

8.7.5 Analysis of Pooled Efficacy and Safety Endpoints

The pooled safety primary endpoints include the number of participants (%) with solicited AEs, unsolicited AEs, MAAEs, SAEs, and AEs leading to discontinuation/withdrawal and will be evaluated in the Pooled SAS and the Pooled RAS.

The pooled efficacy primary endpoint is the incidence rate of virologically confirmed COVID-19. This analysis will be conducted as a sensitivity analysis to the Phase 3b primary endpoint for the study and will be carried out in the Pooled mITT.

The analysis will be conducted using the same methods as described for the Phase 3b primary efficacy analysis (Section 8.7.3.4) and Phase 3b primary safety analysis (Section 8.7.3.2).

Definition and handling of intercurrent events is described in Section 8.3.1.

8.7.6 Analyses of Other Exploratory Endpoints

The analysis of other exploratory endpoints will be described in the SAP.

8.7.7 Other Analyses

Summary statistical analyses will be provided for demographics, medical history, physical examination, social history, and risk factor variables at baseline, as well as vital signs, clinical laboratory tests, etc.

8.7.8 Analyses of Immunogenicity, Safety and Efficacy Data Post Day 92 (Phase 1/2/3a, Phase 3b and Pooled Cohorts)

Participants in Phase 1/2/3a and Phase 3b receive additional study drug (after the initial two-dose vaccination series) at Day 92 (Section 4.5.2). Immunogenicity data before and after Day 92 will be presented separately for these participants.

All safety data collected post Day 92 will be presented separately, using the same methods described in Estimand 2 or 3. Safety data collected post Day 92 include solicited AEs (Phase 2/3a participants only), unsolicited AEs, MAAEs, AEs leading to discontinuation/withdrawal, and SAEs.

Efficacy data after Day 92 will only be collected for Phase 3c participants and will be presented up to Day 394. Rate and 95% CI of the confirmed infection will be calculated using Poisson distribution.

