Study vaccine will be administered in an observer-blind fashion as described in Section [6.3](#). The second study vaccination of each series must be at least 28 days after the first study vaccination. For Phase 1 and 3b, the first Switchover vaccination (Day 92) must be at least 56 days (+30 days) after the second vaccination of the initial series. For Phase 2 and 3a, the 3rd vaccination with study vaccine must be at least 56 days (+30 days) after the second vaccination series.

After receipt of study vaccine in the initial series of vaccinations, the participant will remain under observation for at least 3 hours for Phase 1, and 30 minutes for Phase 3b, and until clinically stable. For Switchover vaccinations, participants in Phase 1 and Phase 3b will be observed for at least 15 minutes and until clinically stable. Participants in Phase 2 and 3a will be observed for at least 30 minutes and until clinically stable for vaccinations 1, 2, and 3 (Day 92) and for at least 15 minutes and until clinically stable for vaccination 4 (Day 120). During the post-vaccination observation period, the participant will undergo assessment of vital signs, body temperature, AEs, and concomitant medications prior to discharge from the clinic.

Should a participant experience a severe AE (including but not limited to hypersensitivity or anaphylaxis) immediately following study vaccine administration, the participant should be observed until clinically stable, and the Clinical Research Organization (CRO) Medical Monitor should be notified immediately. Additional evaluation or testing may be performed based on

discussion between the Medical Monitor and the investigator and subject to Medical Monitor approval.

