4.5.5.7 Vital Signs, Body Temperature, and Pulse Oximetry

Vital signs will be obtained at each clinic visit. Vital signs will be measured in a semi-supine position after 5 minutes of rest and will include systolic and diastolic blood pressure, heart rate, and respiratory rate.

Body temperature will be measured according to standard of care and thermometer instructions. If body temperature is taken orally, the participant should not have consumed hot or cold beverages or smoked within 15 minutes prior to measurement.

Pulse oximetry will be performed at Unscheduled Visits, if warranted, to evaluate symptoms of COVID-19. Vital sign measurements are to be performed by a qualified health care practitioner designated by the investigator.

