Abbreviations: AE=adverse event; COVID-19=coronavirus disease 2019; ET=early termination; MAAE=medically attended adverse event; N/A=not applicable; RT-PCR=reverse transcription polymerase chain reaction; SAE=serious adverse event; SARS-CoV-2=severe acute respiratory syndrome coronavirus 2; TC=telephone call

- a Clinic Visits will be performed in person unless the participant is otherwise directed to remain at home or be seen at a hospital.
- b Unscheduled visits include visits for specific safety issues and/or evaluation of possible COVID-19. These visits may be performed in the clinic, by home visit, by hospital visit (if allowed by local policy), or via telemedicine/telephone visit. Required procedures at these visits include AE and concomitant medication collection. For participants evaluated for COVID-19, samples should be collected for SARS-CoV-2 testing. Should the visit occur in person, the visit should also include evaluation of vital signs, body temperature, pulse oximetry, and symptom-directed physical examination.
- c Screening procedures may be performed on Day 1, if feasible. All Screening procedures must be performed prior to determination of eligibility and enrollment of the participant in the trial. If all Screening procedures are completed on Day 1, the following Screening assessments do not need to be repeated prior to dosing: physical examination, vital signs, body temperature, pregnancy testing, review of COVID-19 symptoms and risks, and collection of AEs and concomitant medications.
- d Complete physical examination will be performed at Screening, Days 1 and 29, 92 and 120 (Switchover/Further Study Vaccine vaccinations), and Final Visit (or ET); symptom-directed examination (if any symptoms) may be performed at other timepoints as indicated to assess changes from Screening.
- e Blood pressure, heart rate, respiratory rate, and body temperature will be measured.
- f Pregnancy testing will be performed on women who are not surgically sterile or postmenopausal. Pregnancy testing by urine dipstick is acceptable. Pregnancy testing will be performed and evaluated prior to each study vaccine administration.

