### 6.6.3 Vital Signs and Physical Examinations

Vital Signs will be analyzed for the following analysis sets:

- Phase 1/2/3a SAS
- Phase 3b SAS
- Phase 3c SAS
- Pooled SAS

Vital signs measured include systolic and diastolic blood pressure, heart rate, and respiratory rate.

Data will be analyzed according to the visit labels as collected. Assessments performed at unscheduled visits will be not included in summary tables but will be included in listings.

The actual value and change from Baseline to each visit (pre-dose assessment, if dosing visit) where assessment was scheduled (including ET visit) will be summarized for systolic and diastolic blood pressure. Summary of post-dose measurements and changes from pre-dose measurement will be done for each time point where pre- and post-dose measurements were performed.

Systolic and diastolic blood pressure will be graded as shown in Table 9. Shift tables from Baseline to each visit and from pre-dose to post-dose will be done.

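### SAP 6.6.3 leaves heart rate and respiratory rate out of its by-visit vital-signs summary, although Protocol 8.7.7 plans summaries of vital signs, and Section 7 does not log the omission

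*Protocol*

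**What the plan says.** Protocol 8.7.7 (Other Analyses) promises summary statistics for a list that includes "risk factor variables at baseline, as well as vital signs, clinical laboratory tests, etc". It names no individual vital sign and no table layout.

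Protocol 4.5.5.7 supplies the content and the frequency: "Vital signs will be obtained at each clinic visit", and these "will include systolic and diastolic blood pressure, heart rate, and respiratory rate". Body temperature has its own paragraph there. The footnote to the schedule in Appendix 1 agrees on what is taken: "Blood pressure, heart rate, respiratory rate, and body temperature will be measured". Measurements are also repeated after vaccination. Under Protocol 4.5.3.2, during the observation period "the participant will undergo assessment of vital signs, body temperature, AEs, and concomitant medications prior to discharge from the clinic".

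SAP 6.6.3 says that vital signs will be analysed in the Phase 1/2/3a, 3b, 3c and Pooled safety sets, and then: "Vital signs measured include systolic and diastolic blood pressure, heart rate, and respiratory rate". The display that follows is narrower. Values and changes from baseline at each visit "where assessment was scheduled (including ET visit) will be summarized for systolic and diastolic blood pressure". The next sentence plans a summary of post-dose values and of their change from pre-dose, without naming a parameter. Grading (SAP Table 9) and the shift tables return to blood pressure.

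**The concern.** Two of the four measurements that the protocol calls vital signs are collected at every clinic visit in a trial of about 19,400 people, and the SAP's main vital-signs table then leaves them out. SAP 1.1 says that the document will set out differences from the protocol. Section 7 does so in detail, down to dropping confidence intervals for adverse event rates, yet it has no entry for this one.

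What is at stake is a by-arm description of heart rate and respiratory rate over time. Both can move in an acute reaction to an injection. The protocol takes such reactions seriously: its Table 1 withholds later doses after anaphylaxis or immediate hypersensitivity of at least moderate severity. Blood pressure does not stand in for them. SAP Table 9 grades raised pressure only, with every systolic value up to 140 mmHg classed as normal, so its shift tables cannot show a fall.

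**Working it through.** The plan states no figure to reproduce. The check is to set the protocol's commitments beside the outputs in SAP 6.6.3 and 6.6.1.1.

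| Measurement | Counted as a vital sign in Protocol 4.5.5.7 | By-visit value and change from baseline | Pre- to post-dose summary | Grading and shift tables |
|---|---|---|---|---|
| Systolic and diastolic pressure | Yes | Yes | Yes, on any reading | Yes |
| Heart rate | Yes | No | Not stated | No |
| Respiratory rate | Yes | No | Not stated | No |
| Body temperature | No, separate paragraph | No | Not stated | No |

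1. *Commitment.* Taken together, Protocol 8.7.7 and 4.5.5.7 promise some summary of heart rate and respiratory rate. They do not clearly promise one of temperature.
2. *By-visit table.* The SAP sentence is expressly limited to blood pressure, so heart rate and respiratory rate are out.
3. *Pre- to post-dose table.* The sentence has no stated subject. It stands between two blood-pressure sentences, which suggests a narrow reading. The section opens with vital signs in general and lists all four, which suggests a wide one. The text does not settle it.
4. *Change log.* None of SAP 7.1, 7.2 and 7.3 has an entry against Protocol 8.7.7 or 4.5.5.7.
5. *Other outputs for heart rate and respiratory rate.* Neither is on the solicited list in SAP 6.6.1.1. Under Protocol 7.4.3 a change leads to an adverse event report if it is judged clinically significant. A modest shift between arms, or an excess of values on which nobody remarked, would not appear in those tables.
6. *Other outputs for temperature.* Fever, categorised by measured temperature, is a solicited event. SAP Table 8 and 6.6.1.1 tabulate it by grade, both within 30 minutes and within 7 days, after Doses 1 and 2 in all phases and after Dose 3 in Phase 2/3a. Not covered are clinic temperature as a measurement, and doses without solicited collection (Dose 3 in Phases 1 and 3b, and Dose 4).

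*What the omitted table could show.* The documents give no standard deviation for a change in heart rate, so 8 to 12 beats per minute is an assumption. With about 8,000 per arm in Phase 3b, the half-width of a 95% interval for the arm difference in mean change is 1.96 × SD × √(2/8000) = 0.0310 × SD:
- SD 8: 0.25 beats per minute
- SD 10: 0.31
- SD 12: 0.37

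This says only that the data could describe a difference precisely. It is not evidence of harm, and attrition by visit would widen the intervals.

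**The case against.** The best defence has three parts.

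*The protocol line is generic.* Protocol 8.7.7 falls under other analyses, ends in an open list, and leaves the detail to the SAP. Vital signs are not an endpoint; the primary safety endpoints are based on adverse events. This stands as a limit on importance. It does not explain why the SAP lists four measurements and then summarises two, without comment in a section written to record such choices.

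*The acute effect may already be covered.* A reader might infer that the SAP summarises blood pressure only and that nothing on heart rate or respiratory rate will be tabulated. The documents do not support that. The pre- to post-dose sentence is not restricted, and it is the table in which a reaction soon after injection would show. This part stands. What is established is omission from the by-visit, grading and shift tables, and uncertainty for the post-dose one.

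*Safety events are captured elsewhere.* Clinically significant changes lead to adverse event reports (Protocol 7.4.3). Events in the observation period that need treatment or longer observation count as medically attended (Protocol 7.4.1.1.4). This is true and lowers the stakes, but such reports depend on judgement in individual cases and do not replace a by-arm summary of the measurements.

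Two further inferences also go too far. One is that temperature is neglected: it is defined apart from vital signs, and graded fever is reported by arm. The other is that, because Phases 1 and 3b keep no diary after Day 92, post-dose vital signs are the only systematic objective safety measure of the first ARCT-154 doses in placebo-first participants. Complete physical examinations are scheduled on Days 92 and 120 (Protocol 4.5.5.5). Adverse events after Doses 3 and 4, and serious and medically attended events from switchover onward, are also tabulated (SAP 6.6.1.2 and 6.6.1.3).

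**Conclusion.** The point holds for heart rate and respiratory rate. Both fall within the protocol's own definition of vital signs and both are collected at every clinic visit. Both are absent from the SAP's by-visit value and change-from-baseline summary, with no logged reason. Whether the pre- to post-dose summary includes them cannot be determined from the text.

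The size is modest: two of four vital signs lack one planned descriptive table and have unclear status in a second. No efficacy result, hypothesis test, primary safety endpoint or sample size depends on it. It is worth correcting because the data exist, the protocol said that they would be summarised, and adverse event reporting answers a different question.

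The conclusion rests on reading vital signs in Protocol 8.7.7 by the definition in 4.5.5.7, and on SAP 6.6.3 being the complete specification of vital-signs tables. It does not rest on the assumed standard deviation.

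**What to change.** In SAP 6.6.3:
- Add heart rate and respiratory rate to the table of values and changes from baseline by visit.
- State that the summary of post-dose values and changes from pre-dose covers systolic and diastolic pressure, heart rate and respiratory rate.
- Keep the analysis sets already listed there.

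Grading and shift tables can stay with blood pressure, because the SAP has no grading scale for the other two. Clinic-measured temperature is an optional extra, given the fever tables. If the sponsor prefers to leave heart rate and respiratory rate out, Section 7 should say so and why.

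A count of participants above a heart-rate or respiratory-rate limit is not proposed. The documents promise no such count and give no limit. SAP 2.4 also records that some of its authors had participant-level unblinded access to Phases 1/2/3a/3b, so a limit chosen now would not be pre-specified there. Plain summaries need no threshold and avoid that problem.

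The cost is a few words of SAP text, two more parameters in an existing table program and a few more pages of output. No new data are needed.

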8.8 Handling of Missing Data

Details regarding handling of missing Diary data for the evaluation of solicited AEs and missing immunogenicity assessments will be described in the SAP.

8.9 Primary and Interim Analyses Timepoints

8.9.1 Phase 1/2/3a Substudy

The primary immunogenicity analysis for Phase 1/2/3a will be performed after all participants in this cohort reach the Day 57 timepoint.

The primary Phase 1/2/3a analysis of safety will be performed when all participants in this cohort have reached Day 92. Subsequent analyses of safety will be exploratory.

Interim analysis of safety data through at least Day 57 may be performed for Phase 1/2/3a at the time of analysis of the primary immunogenicity endpoint of Phase 1/2/3a to support application for emergency use authorization. Participants that are further randomized to receive ARCT-154 or placebo at Day 92 may be unblinded again at Day 120 for evaluation of safety and immunogenicity following the third dose. Sponsor and CRO staff responsible for day-to-day conduct of the study will remain blinded until the final unblinding of data at the end of study occurs in order that safety assessments can continue in an unbiased fashion.

